Trial design: Open label, single cohort proof of concept trial. An additional arm of the study will be for subjects treated with the study drug in malignant pituitary tumors. Three clinical trial sites, one at CSMC and the others at Johns Hopkins Hospital and Massachusetts General Hospital.

Study population: Patients will be recruited from the Pituitary Center at Cedars-Sinai Medical Center and the other two sites.

Intervention: lapatinib 1250 mg daily for 6 months. Patients will be treated with the standardized dose used in breast cancer therapy for six months (Cameron & Stein 2008; Geyer et al. 2006). The drug will be supplied by Novartis Oncology.

- a. Primary outcome variable.

Primary outcome in nonfunctioning pituitary adenomas: 40% reduction in tumor size in any dimension. Tumor size and volume will be calculated using Open Source OsiriX® Imaging Software for MacOS. MRIs will be performed at baseline and at 3 and 6 months All MRIs will be centrally read by the dedicated pituitary radiologist at CSMC.

Primary outcome in prolactinomas: 40% reduction in tumor size in any dimension.

Primary outcome in malignant pituitary tumors: Progression free survival

- b. Secondary outcome variables.

Secondary outcomes in prolactinomas:

(a) achievement of 50% reduction of PRL levels (b) PRL normalization (c) percent reduction in PRL levels (d) percent reduction in tumor volume. Tumor volume will be calculated using Open Source OsiriX® Imaging Software for MacOS. (e) correlation of tumor size and PRL reduction (f) clinical predictors of TKI response, including age, gender, duration of disease, dose and duration of dopamine agonist therapy, baseline PRL, and baseline tumor size.

Secondary outcomes in malignant pituitary tumors: partial response, complete response, mortality, 24 hour urine free cortisol levels for Cushing carcinomas, IGF-1 levels for acromegaly carcinomas.

We will correlate ErbB receptor expression with the subjects' clinical response to the study drug. This will be performed through immunohistochemistry staining of pituitary tumor slides from surgery.

Section 5.0. Selection and Withdrawal of Subjects

Inclusion criteria: Subjects with non-functioning pituitary adenomas, who have undergone at least one prior surgical resection and have demonstrated recurrence on MRI.

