Subjects with prolactinomas who are resistant to dopamine agonist therapy who manifest continued tumor size growth while on a dopamine agonist, unless intolerant of adequate doses of a dopamine agonist.

Subjects with malignant pituitary tumors will be eligible for the malignant pituitary tumor arm of the study regardless of existing visual deficits.

Exclusion criteria: Children will be excluded. If subjects have preexisting visual field deficits, they will be monitored on more frequent basis. Patients will also be excluded if they have left ventricular ejection fraction less than 50 %, moderate to severe hepatic impairment (see below for specifics), active hepatitis, HIV positivity, concurrent cancers, life expectancy less than one year, and pregnancy. Pregnant patients will be excluded. Childbearing age women will be required to use

contraception. Patients who become pregnant during the study should discontinue the study immediately.

Withdrawal of Subjects:

Monitoring for adverse effects: Prior to initiating therapy, patients will undergo an echocardiogram and ECG to evaluate the ejection fraction, and the echocardiogram will be repeated every 8 weeks (Visit 3, 5, and 7) and on visit 8. Patients will also undergo ophthalmic testing at visits 1, 4, and 7. Patients with pre-existing stable visual field compromise prior to enrollment will undergo visual field testing at visits 1, 2, and 3, and if stable, then they will proceed with visual field testing every three months for the duration of the study. Patients will be evaluated for adverse effects monthly with physical examinations, chemistry and hematology panels, and ECGs. Adverse events will be graded by the NCI-CTC and include: anorexia, decreased ejection fraction, interstitial lung disease/pneumonitis, diarrhea, nausea, vomiting, hepatotoxicity, rash, and fatigue. Lapatinib will be discontinued in those who developed decreased ejection fraction, who develop pulmonary symptoms, retinal toxicity, worsening of visual fields, and those with toxicity greater than or equal to Grade 2 on the NCI-CTC. [name], from Oncology department at Cedars-Sinai Medical Center, will assist us in monitoring patients for adverse events.

If at any time a patient demonstrates compromise of his visual fields, dilated retinal exam or tumor growth on MRI, he will be withdrawn from the study and referred for surgery.

Section 6.0 Treatment of Subjects

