MRI—this will be waived if subjects had an MRI performed at their outside hospital within 3 months of the 1st study visit and if subjects provide a CD of the images for review by our neuroradiologist to determine if of sufficient quality for a baseline study.

While on the drug, visits will occur once a month to monitor for adverse effects. Patients' visits may not deviate more than 7 days from the 30-day mark between each visit.

Visit 2: time 1 month on drug

Physical exam and history

Will draw CBC with differential, BMP, LFTs (15 cc blood)

For those with prolactinomas, will also check PRL.

For those with acromegaly from malignant tumors, will GH levels on 2 hour OGTT

For those with ACTH secreting malignant tumors, will check 24 hour urinary free cortisol

Do ECG

Urine Pregnancy Test

Those with pre-existing visual field compromise, visual field testing

Visit 3: time 2 months on drug

Physical exam and history

Will draw CBC with differential, BMP, LFTs (15 cc blood)

For those with prolactinomas, will also check PRL.

For those with acromegaly from malignant tumors, will check GH levels on 2 hour OGTT

For those with ACTH secreting malignant tumors, will check 24 hour urinary free cortisol

Those with pre-existing visual field compromise, visual field testing

Do ECG, echocardiogram

Urine Pregnancy Test

Visit 4: time of 3 months on drug

Physical exam and history

Will draw CBC with differential, BMP, LFTs (15 cc blood)

For those with prolactinomas, will also check PRL.

For those with acromegaly from malignant tumors, will check GH levels on 2 hour OGTT

For those with ACTH secreting malignant tumors, will check 24 hour urinary free cortisol

Pituitary hormones as well—TSH, thyroid panel, free T4, 8 am cortisol (if indicated), IGF-1, LH, FSH, testosterone (15 cc blood)

Tubes for lab for EGFR, her2 levels (10 cc blood)

Do ECG
Visual field test
Dilated retinal exam
Color Vision test
Do MRI of pituitary with and without IV gadolinium
Urine Pregnancy Test

Visit 5: time of 4 months on drug
Physical exam and history
Will draw CBC with differential, BMP, LFTs (15 cc blood)
For those with prolactinomas, will also check PRL.
For those with acromegaly from malignant tumors, will check GH levels on 2 hour OGTT
For those with ACTH secreting malignant tumors, will check 24 hour urinary free cortisol
Do ECG, echocardiogram
Urine Pregnancy Test

Visit 6: time of 5 months on drug
Physical exam and history

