Pregnancy Test for pre-menopausal women	X	X	X	X	X	X	X	X

^ Only for subjects with visual field deficits

^^ will be waived if subjects had MRI at outside hospital within 3 months of baseline visit

* Only for subjects with acromegaly from malignant tumors

+Only for subjects with ACTH secreting adenomas from malignant tumors

**Visit 8 is only required if stopping Lapatinib at visit 7. Patients continuing on Lapatinib after visit 7 will be followed by their physician as clinically appropriate.

Section 7.0 Assessment of Efficacy

a. Primary outcome variable.

Primary outcome in nonfunctioning pituitary adenomas: 40% reduction in tumor size in any dimension. Tumor size and volume will be calculated using Open Source OsiriX® Imaging Software for MacOS. MRIs will be performed at baseline and at 3 and 6 months All MRIs will be centrally read by the dedicated pituitary radiologist at CSMC.

Primary outcome in prolactinomas: 40% reduction in tumor size in any dimension.

Primary outcome in malignant pituitary tumors: Progression free survival

b. Secondary outcome variables.

Secondary outcomes in prolactinomas:

(a) achievement of 50% reduction of PRL levels (b) PRL normalization (c) percent reduction in PRL levels (d) percent reduction in tumor volume. Tumor volume will be calculated using Open Source OsiriX® Imaging Software for MacOS. (e) correlation of tumor size and PRL reduction (f) clinical predictors of TKI response, including age, gender, duration of disease, dose and duration of dopamine agonist therapy, baseline PRL, and baseline tumor size.

Secondary outcomes in malignant pituitary tumors: partial response, complete response, mortality, 24 hour urine free cortisol levels for Cushing carcinomas, IGF-1 levels for acromegaly carcinomas

We will correlate ErbB receptor expression with the subjects' clinical response to the study drug. This will be performed through immunohistochemistry staining of pituitary tumor slides from surgery.

Section 8.0 Assessment of Safety

1. *Monitoring for adverse effects (further detailed below):* Data has been collected on over 12000 subjects on combination therapy of lapatinib and other chemotherapies, and over 4000 subjects have been treated with lapatinib monotherapy, with 2347 of those specifically in breast cancer. With monotherapy, majority of AEs were Grade 1 or 2 in severity. The incidence of Grade 3 and Grade 4 events was 21% in those

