Tumor maximal size will be obtained at baseline, 3 months, 6 months after initiation of treatment. The primary hypothesis is the change from baseline to 6 months. The analysis using maximal resistant tumor size will be carried out for the specified times given above. Initially this will be by descriptive analytic and then by inferential analysis using the test for change between baseline and 6 months and change between baseline and 3 months using rank test. We will also use Hotelling's T^2 to combine both pre-post changes.

This study is in the clinical trials paradigm essentially a Phase IIa trial and thus use of alpha type 1 error is at 10%. This is sanctioned by the biostatistics section of NCI.⁴⁰ We will also analyze the secondary endpoints of Aim 1 according to the above models. Concepts behind analysis for quantitative and binary are the same though the methods are different.

Our overall target sample size is 30 subjects which includes nonfunctioning adenomas and prolactinomas, 15 to be recruited from Cedars Sinai Medical Center and 15 from Johns Hopkins Hospital and Massachusetts General Hospital. We aim to recruit 24 subjects with prolactinomas and 6 nonfunctioning adenomas.

Due to the rarity of pituitary tumors in the general population and even more rare are aggressive pituitary tumors such as we propose to study, it is difficult to do a randomized placebo controlled trial with sufficient sample size numbers to achieve adequate power. By using the subjects as their own controls, we alleviate the issues with recruitment. This is a safety and activity trial to look for a sufficient effect of the drug on tumor growth before proceeding to a larger, randomized placebo controlled trial.

Section 10.0. Quality Control and Quality Assurance

Only samples and data collected with appropriate consent will be used for the proposed analysis. Specimens and data collected under the proof of concept clinical trial of lapatinib will be coded in such a way so that other members of the research team will be unable to ascertain the identity of specific patients. All of our data will be

RECOMMENDED ELEMENTS OF A SCIENTIFIC PROTOCOL
(Noted sections should only be included as applicable to your research)

38

maintained confidentially. Data will be kept in locked file cabinets and in password protected files on computer systems.

Section 11.0 Ethical considerations relating to the trial

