Subjects will be recruited from the Pituitary Center. They will be patients followed clinically. Patients will be approached regarding participation in the study and given consent forms to review at home. They will be reassured that their clinical care will not be affected if they choose not to participate. Patients will be given opportunities to ask questions and review the consent process. Once they consent and enroll in the study, their data will be deidentified for the duration of the study. All patients entering the trial will be given the study drug. There is no placebo arm. The risks of the study are related to the side effects of the study drug and patients will be monitored for this and informed on the effects. The benefits of the study are stabilization of tumor growth. There are potential conflicts of interest between the patient's need for surgical referral and participation in the research study. However, by excluding patients who would meet definite criteria for surgery, we will minimize the conflict of interest.

Section 12.0 Data Handling and Recordkeeping

Data will be maintained in separate research charts in a locked cabinet in a locked office.

The data will be entered as well into an electronic database on a password protected computer. Only study staff and the investigators will have access to these records.

Section 13.0 Financing and Insurance

Funding for this study will be through institutional funds. Patients will only be charged for the initial MRI and visual field test, as well as hormonal tests during the study period.

Section 14.0 Publication Policy

We intend to submit our research findings to relevant peer-reviewed journals for publication. We will submit data for presentation at international meetings. We will adhere to the NIH Grants Policy Statement on Sharing of Biomedical Research Resources, including the "Principles and Guidelines for Recipients of NIH Research Grants and Contracts on Obtaining and Disseminating Biomedical Research Resources: Final Notice" (64FR 72090, December 23, 1999; and described at <http://ott.od.nih.gov/NewPages/RTguide/final.html>).

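### For patients who use the MRI waiver, the baseline scan can predate Visit 1 by up to 3 months and can be the scan that qualified them, so untreated time can enter the primary change.

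*Combined protocol and SAP*

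**What the plan says.** All references are to the combined protocol and SAP.

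- **Section 6.0, baseline Visit 1.** An MRI is listed at time 0, but "this will be waived if subjects had an MRI performed at their outside hospital within 3 months of the 1st study visit". The only other condition is that the patient brings the outside images on disc and the site's neuroradiologist finds them good enough to serve as baseline. The flowsheet footnote repeats the rule without the quality condition: it "will be waived if subjects had MRI at outside hospital within 3 months of baseline visit".
- **Section 6.0, start of treatment.** Patients who meet the criteria at Visit 1 go on to start the drug. No maximum interval is given from Visit 1, or from the MRI, to the first dose. The month 3 and month 6 MRIs are specified with and without gadolinium.
- **Section 5.0.** Patients with nonfunctioning adenomas must "have demonstrated recurrence on MRI". Prolactinoma patients are those "who manifest continued tumor size growth while on a dopamine agonist, unless intolerant of adequate doses of a dopamine agonist". Neither criterion dates the qualifying scan or separates it from the baseline scan.
- **Section 7.0.** The primary outcome in both tumour types is a 40% reduction in any dimension, with central reading of all MRIs.
- **Section 9.0.** "The primary hypothesis is the change from baseline to 6 months". Patients serve as their own controls. The changes to months 3 and 6 are analysed by a rank test and combined in Hotelling's T².

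**The concern.** Without a concurrent control, the baseline scan carries the whole comparison. If it is an outside scan taken well before treatment, the recorded change mixes an untreated period with the treated one. Patients are mostly enrolled because their tumour recurred or kept growing, so that untreated period need not be neutral.

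Two effects can follow, and they pull in opposite directions. Growth between the old scan and the first dose is counted against the drug. If instead the baseline is the scan that showed the qualifying growth, it was chosen partly because it read large, and regression to the mean can make later scans look smaller. Section 9.0 uses the same baseline for both the month 3 and month 6 changes, so an error in it enters both.

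**Working it through.** **1. The plan's own figure.** Inputs from Section 9.0: null rate 20%, alternative 40%, one-sided exact binomial test, alpha 0.10, power 80%. The smallest N with P(X ≥ r | 0.20) ≤ 0.10 and P(X ≥ r | 0.40) ≥ 0.80 is N = 24 with r = 8, giving exact alpha 0.0892 and power 0.8081. The stated 24 is reproduced. This point does not change it.

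**2. Share of the interval that can be untreated.** Take 3 months as 90 days, place months 3 and 6 at +90 and +180 days as in the flowsheet, and assume dosing starts at Visit 1. For the oldest scan allowed:

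- baseline to month 3: 90 / (90 + 90) = 90/180 = 50%
- baseline to month 6: 90 / (90 + 180) = 90/270 = 33%

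For a patient scanned at Visit 1, both shares are about zero.

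**3. Effect of pre-dose growth on the 40% criterion.** The documents give no growth rate, so linear growth g from the old scan to first dose is assumed over 0–20%. A true 40% on-drug reduction is recorded as 1 − 0.6(1 + g). The on-drug reduction needed to record 40% is 1 − 0.6/(1 + g).

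| g (assumed) | True 40% reads as | On-drug fall needed |
|---|---|---|
| 0% | 40% | 40.0% |
| 5% | 37% | 42.9% |
| 10% | 34% | 45.5% |
| 20% | 28% | 50.0% |

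Only waived patients whose true fall lies between 40% and the last column are reclassified. At g = 5% that band is under 3 percentage points wide (42.9 − 40.0 = 2.9).

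**4. Effect on continuous change.** Here no threshold absorbs the error. A tumour unchanged on drug is recorded as having grown by g: 5%, 10% or 20% on the same assumptions. Every waived patient's value is shifted, not only those near a cut-off.

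**5. Opposite direction.** If the qualifying scan is reused as baseline, the expected measurement error in it is positive among patients selected on apparent growth, so part of the later fall can be spurious. The documents give no measurement error, so only the direction is claimed.

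**6. Sensitivity of the 8-of-24 rule.** If a true response rate of 0.40 were recorded as 0.38, power would be 0.749; if a null rate of 0.20 were recorded as 0.22, the false-positive rate would be 0.138. These shifts are chosen for illustration. The size of any real shift depends on how many patients are waived, which the documents do not say.

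**The case against.** The strongest reply is that the default is a Visit 1 MRI, the waived scan is reviewed for quality, all scans are centrally read, and a 40% reduction is a high bar in tumours that the background section describes as mostly slow-growing. Much of this stands. It limits the point to waived patients and makes the effect on the responder endpoint probably modest. It does not settle timing or selection: quality review and central reading address neither, and the background section also describes rapid growth in aggressive adenomas.

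A further fair reply is that Visit 1 itself determines eligibility, so a Visit 1 MRI could also be the scan that shows growth. That is right, and a rule restricted to outside scans does not remove that route. Prolactinoma patients admitted for dopamine agonist intolerance also appear not to need documented growth, so the selection effect may not apply to them.

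Several stronger readings are tempting but not supported:

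- **The waiver will be common.** Section 13.0 says "Patients will only be charged for the initial MRI and visual field test", and candidates are already followed with serial MRIs, so use is plausible. No frequency is given.
- **Pre-dose growth will trigger withdrawal at month 3.** Sections 5.0 and 8.0 give neither a growth threshold nor a reference scan, so this cannot be determined; small apparent growth could also be measurement noise.
- **Drug wash-out lengthens the untreated share further.** Wash-out could precede Visit 1, and any delay after it would affect a Visit 1 MRI equally.
- **Outside scanners or sequences bias the comparison.** No scanner or sequence is fixed for any MRI at the three sites, so this is not specific to the waiver.
- **The regression effect has a known size.** A formula such as SD/√π holds only for a tumour with no true growth that qualified solely because the second of two equally noisy scans read larger.

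**Conclusion.** The point holds for patients who use the waiver. A rule followed exactly as written can make half of the month 3 interval and a third of the month 6 interval untreated, and can make the qualifying scan the baseline. Those shares are the maximum, for a 90-day-old scan with dosing at Visit 1.

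The net direction of bias is not fixed, and without a control arm the two effects cannot be separated. Its size rests on assumed growth rates and on an unknown number of waived patients. The rank and Hotelling's T² analyses are more exposed than the 40% responder endpoint. Read as a claim that the primary change fails to start at treatment for the whole trial, it would go too far: patients scanned at Visit 1 are largely unaffected. This is an inexpensive improvement to the baseline definition, not a flaw in the sample size.

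**What to change.** In the Visit 1 MRI paragraph and the flowsheet footnote of Section 6.0:

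- Count the window back from the first dose and shorten it. About 4 weeks is an example; the documents give no basis for an exact length, so the sponsor should set it.
- Accept an outside scan only if it includes gadolinium, as the month 3 and 6 scans do, and is not the scan used to show recurrence or growth.
- Otherwise perform the Visit 1 MRI already in the schedule.

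In Section 9.0, record the scan-to-first-dose interval for every patient and repeat the primary analysis excluding waived baselines.

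The cost is an edit to one paragraph and one footnote plus an added analysis, with no extra patients or visits. The downside is that some patients lose the waiver and need an MRI they would have avoided. Section 13.0 currently charges patients for the initial MRI, so that charge must be reconsidered, and any cost taken off them falls on the study's institutional funds.

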Will draw CBC with differential, BMP, LFTs (15 cc blood)
For those with prolactinomas, will also check PRL.
For those with acromegaly from malignant tumors, will check GH levels on 2 hour OGTT
For those with ACTH secreting malignant tumors, will check 24 hour urinary free cortisol
Do ECG
Urine Pregnancy Test
Those with pre-existing visual field compromise, visual field testing

Visit 7: time of 6 months on drug
Physical exam and history
Will draw CBC with differential, BMP, LFTs (15 cc blood)
For those with acromegaly from malignant tumors, will check GH levels on 2 hour OGTT
For those with ACTH secreting malignant tumors, will check 24 hour urinary free cortisol
Pituitary hormones as well—PRL, TSH, thyroid panel, free T4, 8 am cortisol (if indicated), IGF-1, LH, FSH, total and free testosterone for males (15 cc blood)
Tubes for lab for EGFR, her2 levels (10 cc blood)
Do ECG, Echocardiogram
Check visual fields
Dilated retinal exam
Visual acuity check
Ocular pressure check
Color Vision test
Do MRI of pituitary with and without IV gadolinium
Urine Pregnancy Test

Visit 8: time of 1 mo off drug
Physical exam and history
Will draw CBC with differential, BMP, LFTs (15 cc blood)
For those with prolactinomas, will also check PRL.
For those with acromegaly from malignant tumors, will check GH levels on 2 hour OGTT
For those with ACTH secreting malignant tumors, will check 24 hour urinary free cortisol
Draw tubes for EGFR, Her2 levels (10 cc blood)
Do ECG, Echocardiogram

Urine Pregnancy Test

Note: Study visits may be conducted over 2 days to allow for sufficient time to complete the procedures, scheduling availability, and patient preference.

Study procedure flowsheet:

(See following page)

Procedure	Baseline Visit	Visit #2 (+30 days)	Visit #3 (+60 days)	Visit #4 (+90 days)	Visit #5 (+120 days)	Visit #6 (+150 days)	Visit #7 (+180 days)	Visit #8** (+210 days)
Laboratory Blood Tests (may include levels of hormones, cholesterol, CBC, and metabolic panel)	X	X	X	X	X	X	X	X
MRI of the Pituitary	X^^			X			X	
Echocardiogram	X		X		X		X	X
Electrocardiogram (ECG)	X	X	X	X	X	X	X	X
Visual Field Test	X	X^	X^	X		X^	X	
History and Physical	X	X	X	X	X	X	X	X
Informed Consent	X							
Color Vision Test	X			X			X	
Ocular Pressure Check	X						X	
Visual Acuity	X						X	
Dilated Retinal Exam	X			X			X	
Hormonal profile	X	X	X	X	X	X	X	X
Oral Glucose Tolerance Test (OGTT) (malignant arm)	X*	X*	X*	X*	X*	X*	X*	X*

24-hour Urinary Free Cortisol (malignant arm)	X+							

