Record the appearance or worsening of clinical symptoms of hepatitis, or hypersensitivity, fatigue, decreased appetite, nausea, vomiting, abdominal pain, jaundice, fever, or rash as relevant on an AE report form;

Record use of concomitant medications, acetaminophen, herbal remedies, other over the counter medications, or putative hepatotoxins, on the concomitant medications report form;

Record alcohol use on the liver event alcohol intake case report form.

Refer to Appendix 3 for a liver safety algorithm detailing stopping and follow up criteria.

Safety

Add frequency of LFTs to Safety Assessment section and Time & Events Table as applicable:

- During treatment phase: every 4 - 6 weeks (to best fit protocol schedule) for duration of concurrent chemotherapy administration or for first 6 months, then

every 8 – 12 weeks (or more frequently, if clinically indicated) for remaining on treatment period

- During post-treatment phase: continue to monitor any liver chemistry abnormalities noted during treatment or within 30 days after last dose of investigational product until values return to normal or baseline (this language should be in protocols already)

In the Safety Assessment section, make a reference to section containing the Liver Chemistry Stopping and Follow up Criteria.

In the Laboratory Assessment section, mention that bilirubin fractionation is recommended if total bilirubin $>2 \times$ ULN when testing is available.

[figure not shown]
Hepatobiliary events have been seen in subjects taking lapatinib and other tyrosine kinase inhibitors. As a precaution, the following will be reported as an SAE:

- ALT $>3 \times$ ULN and total bilirubin $>2.0 \times$ ULN ($>35\%$ direct; bilirubin fractionation required).

NOTE: bilirubin fractionation should be performed if testing is available. If testing is unavailable and a subject meets the criterion of total bilirubin $>2.0 \times$ ULN, then the event should still be reported as an SAE.

Other hepatic events should be documented as an AE or an SAE as appropriate.

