Pregnancy	2 Weeks	Pregnancy Notification Form	2 Weeks	Pregnancy Follow up Form
Liver chemistry abnormalities:				
ALT $>3 \times \text{ULN}$ and bilirubin ^a $>2 \times \text{ULN}$ (35% direct)	24 hours	CRF	24 hours	CRF

- a. bilirubin fractionation should be performed if testing is available. If testing is unavailable and a subject meets the criterion of total bilirubin $>2.0 \times \text{ULN}$, then the event should still be promptly reported as defined.

Reporting Serious Adverse Events

Any serious adverse events which occur during the clinical study or within 30 days of receiving the last dose of study medication, whether or not related to the study drug, must be reported by the investigator. In addition, any SAEs which occur as a result of protocol specific diagnostic procedures or interventions must also be reported.

The principal investigator has the obligation to report all serious adverse events to the FDA, IRB, and Novartis Pharmaceuticals Drug Safety and Epidemiology Department (DS&E) (***For patients taking Lapatinib / Novartis drugs***).

All events reported to the FDA by the investigator are to be filed utilizing the Form FDA 3500A (MedWatch Form).

To ensure patient safety, every SAE, regardless of suspected causality, occurring

- after the patient has provided informed consent and until at least 30 days after the patient has stopped study treatment/participation
- after protocol-specified procedures begin (e.g., placebo run-in, washout period, double-blind treatment, etc.) and 30 days after the patient has stopped study treatment

RECOMMENDED ELEMENTS OF A SCIENTIFIC PROTOCOL
(Noted sections should only be included as applicable to your research)

35

- after the start of any period in which the study protocol interferes with the standard medical treatment given to a patient (e.g., treatment withdrawal during washout period, change in treatment to a fixed dose of concomitant medication) and until 30 days after the patient has stopped study treatment

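### The flowsheet footnote on Visit 8 conflicts with the visit list and the liver rules and, read literally, leaves most non-hepatic early stoppers without a scheduled off-drug safety visit

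*Combined protocol and SAP*

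**What the plan says.** Section 6.0 describes Visit 8 twice. The visit list heads it "Visit 8: time of 1 mo off drug", with no condition on when lapatinib was stopped. Its content includes history and examination, CBC, BMP, LFTs, ECG, echocardiogram and pregnancy test. The flowsheet puts Visit 7 at day 180 and Visit 8 at day 210. Its footnote says "Visit 8 is only required if stopping Lapatinib at visit 7" and then "Patients continuing on Lapatinib after visit 7 will be followed by their physician as clinically appropriate". Patients who stop before Visit 7 are not mentioned. Monthly visits are tied to being on the drug.

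Sections 5.0 and 8.0 give several routes to an early stop. For a patient with visual compromise, a retinal finding or growth on MRI, Section 5.0 says "he will be withdrawn from the study and referred for surgery". Section 8.0 repeats this for visual fields and growth, and also ends treatment for Grade 4 toxicity and for a confirmed, persistent LVEF fall. None of these passages sets an early-termination visit.

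Two rules under Liver Chemistry Stopping Criteria point the other way. One keeps permanent liver stoppers on the study assessments of a Time & Events Table (its section number is an unfilled placeholder), with weekly liver chemistry. The other cancels Visit 8 for a patient restarted after a liver hold who decides to continue lapatinib before discontinuing it on study.

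The follow-up windows differ by event type. General adverse events are recorded until five days after the last dose. The serious-event rule covers "Any serious adverse events which occur during the clinical study or within 30 days of receiving the last dose of study medication". The LFT instruction for the post-treatment phase is to "continue to monitor any liver chemistry abnormalities noted during treatment or within 30 days after last dose of investigational product".

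**The concern.** Section 9.0 presents this as a safety and activity trial, so off-drug safety data are part of what it is meant to deliver. If sites follow the footnote as written, whether a patient has the off-drug visit depends on why and when treatment ended. A patient who stops at six months is examined and tested a month later. A patient withdrawn at three months for growth or vision is not.

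This matters because three of the protocol's own serious-event definitions rest on test results: an LVEF fall of at least 20% to below the institutional lower limit, ALT above 3 times ULN with bilirubin above 2 times ULN, and any Grade 4 laboratory abnormality (Section 8.0, Cardiac Events and Additional SAE definitions). For early stoppers outside the liver rules, a reporting window is open but no test is scheduled in it. A new asymptomatic event could go unrecorded.

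**Working it through.** **1. Timing of Visit 8.** Inputs are the flowsheet days. The plan's figure reproduces for a stop at Visit 7: 180 + 30 = 210. For earlier stops, time off drug at a fixed day 210 is 210 minus the stop day. Echocardiograms fall at baseline and at days 60, 120, 180 and 210.

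| Stop at | Day | Days off drug at day 210 | Last scheduled echocardiogram (day) | Gap from echocardiogram to stop (days) |
|---|---|---|---|---|
| Visit 2 | 30 | 180 | baseline | about 30 |
| Visit 3 | 60 | 150 | 60 | 0 |
| Visit 4 | 90 | 120 | 60 | 30 |
| Visit 5 | 120 | 90 | 120 | 0 |
| Visit 6 | 150 | 60 | 120 | 30 |
| Visit 7 | 180 | 30 | 180 | 0 |

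Visits may shift by 7 days, so the 30-day gaps are approximate. In every row before Visit 7, a fixed day 210 falls outside the 30-day serious-event window. The visit list and the flowsheet therefore agree only for a stop at Visit 7. Timed from the last dose, as the visit list allows, the visit would fall at about 30 days for everyone.

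**2. Where early stops are likely to be triggered.** On-study MRIs are at Visits 4 and 7, so growth found on a scheduled scan before completion is found at Visit 4. That visit has no echocardiogram, so the last scheduled one was at about day 60. Visual fields are tested in all patients at Visit 4, and in those with existing deficits also at Visits 2, 3 and 6. Of these four visits, only Visit 3 includes an echocardiogram.

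**3. Off-drug assessment by group, reading the footnote literally.**

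- Stop at Visit 7: Visit 8 is required.
- Continue after Visit 7: exempt, and followed by their own physician.
- Permanent liver stop: weekly liver chemistry and continued study assessments, although the cross-reference is unfilled and the only schedule supplied is the one carrying the footnote.
- Asymptomatic LVEF fall: the fall is confirmed on drug, treatment is interrupted and recovery is assessed over the next three weeks. No echocardiogram is set after permanent withdrawal.
- Early stop for vision, growth or other non-hepatic toxicity: no scheduled examination, laboratory tests, ECG or echocardiogram.

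**4. Number affected.** The target is 30 patients (24 prolactinomas and 6 nonfunctioning adenomas, Section 9.0); no number is given for the malignant arm. The documents state no early-stop rate, so 10% to 40% is assumed: 0.10 × 30 = 3 and 0.40 × 30 = 12. This counts all early stops, including liver stops, who do have some follow-up.

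**The case against.** The best defence is that the footnote is loosely worded and no omission was intended. Its second sentence concerns patients who stay on lapatinib, the visit list has no Visit 7 condition, and cancelling Visit 8 after a liver hold makes sense only if the visit otherwise follows an early stop. As a reading of intent this is plausible, and it is why the point is a conflict between passages and not a settled decision to skip the visit. It does not remove the defect, because the footnote governs the schedule that sites will use.

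The second defence is that other duties apply. Adverse events are followed until they subside or stabilise, investigators may order extra laboratory tests, serious events are reportable for 30 days, and related ones at any later time. All of that stands. But follow-up attaches to events already detected, the extra testing is discretionary and mentions only laboratory work, and none of these duties fixes a visit.

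Third, few events are at stake. At the roughly 1% cardiac rate in Section 8.0, 30 patients would yield 30 × 0.01 = 0.3 events over the whole trial. That is fair: the problem is the pattern of missing safety data, not a large expected count.

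A reader might infer four stronger things that the documents do not support:

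- That no early stopper has any off-drug check. The liver and LVEF rules contradict this.
- That off-drug data would be complete for six-month completers and absent for those stopped for harm. Completers who continue lapatinib also skip Visit 8, and the liver and LVEF groups are followed.
- That late events could not be found. They have no scheduled test, but symptoms or discretionary laboratory tests may reveal them.
- That the 21% Grade 3-4 incidence implies about 6 of 30 early stops (0.21 × 30 = 6.3). It is an incidence of events, not of stopping. Section 8.0 holds and resumes treatment at Grade 3 and ends it at Grade 4, while Section 5.0 ends it from Grade 2. Those rules need reconciling themselves, and neither makes 21% a stop rate.

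**Conclusion.** The concern holds as an internal conflict with a practical consequence. The footnote disagrees with the visit list, with the continued-assessment rule for liver stoppers and with the Visit 8 exemption after a liver hold. Followed literally, it removes the only scheduled off-drug safety visit for patients who stop before Visit 7 for vision, growth or non-hepatic toxicity, subject to the interim LVEF assessment described above.

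The size is uncertain: 3 to 12 of 30 patients, resting entirely on the assumed 10% to 40% early-stop rate and counting missed visits, not missed events. Confidence is high on the wording and on the absence of an early-termination visit, and lower on how much safety information would be lost. The point should be corrected because the trial describes itself as assessing safety and the correction is small. It has no bearing on the sample size, power or the primary endpoint.

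**What to change.** Reconcile the flowsheet footnote with the visit list and the two liver rules. For complete safety data, the footnote would exempt only patients who continue lapatinib. The protocol's own visit at one month off drug, timed from the last dose and not from day 210, would apply to everyone who permanently stops at or before Visit 7, whatever the reason. Fill in the placeholder cross-references in the liver section so that they point to the same schedule.

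Add one sentence to each of Sections 5.0 and 8.0 stating that withdrawal from treatment, including referral for surgery, does not end safety data collection at that visit. If the sponsor does intend early stoppers to have no such visit, the protocol should say so and list it as a limitation of the safety data.

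The cost is an amendment to one footnote and a few sentences, using a visit already planned. No dose or stopping rule changes. The downside is that some early stoppers will decline or be in surgical care, so attendance should be reported by reason for stopping.
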